4.2. Study Treatments

The overall study design is presented in [Figure 1](#).

Per Protocol Amendment 7, Phase 2 Dose Expansion Phase will not proceed.

Figure 1: Overall Study Design

[figure not shown]
[figure not shown]

Figure 1: Overall Study Design (continued)

Arm A (Single agent CC-122):

Subjects assigned to Arm A will be administered a starting dose of 1.0 mg CC-122 orally on a 5/7-day (5 continuous days out of 7 days per week) schedule starting at Cycle 1 Day 1 up to a maximum of 24 cycles of each cycle with intrasubject dose escalation permitted up to a maximum dose of 4.0 mg until PD, unacceptable toxicity or discontinuation for any other reason. Each subject will be permitted to dose escalate by 0.5 mg increments every 2 weeks based on investigator assessment of the individual subject's tolerability. Subjects will have the option to receive the addition of ibrutinib or obinutuzumab if there is evidence of PD while on CC-122 monotherapy after the completion of the DLT evaluation and CC-122 in combination with these standard agents has been demonstrated to be safe in the context of this trial. Each cycle consists of 28 days.

Subjects who are enrolled to fixed dose cohorts (0.25 mg or 0.5 mg daily) in Arm A under earlier protocol amendments (i.e., protocol amendment 3 or 4) will be allowed to undertake intrasubject dose escalations as described above. Those subjects will switch to a 5/7 schedule as soon as the protocol amendment 5 has been approved at their site.

Arm B (CC-122 + ibrutinib):

Subjects in Arm B will be administered CC-122 orally on a 5/7-day schedule starting on Cycle 2 Day 1. CC-122 will be initiated until PD, unacceptable toxicity or discontinuation for any reason.

Subjects will take orally three 140 mg capsules of ibrutinib daily for a total dose of 420 mg. Ibrutinib will be administered daily starting Cycle 1 Day 1 up to a maximum of 24 cycles of CC-122 until PD, unacceptable toxicity or discontinuation for any other reason. For subjects who discontinue CC-122 prior to 24 cycles or if subjects have surpassed the 24 cycles of CC-122, Celgene will continue to provide an additional 3 cycles of ibrutinib from the investigational supply to allow time for subjects to be switched to commercially available ibrutinib and/or other therapies at the discretion of the treating physician.

Arm C (CC-122 + obinutuzumab):

Subjects in Arm C will be administered CC-122 orally on a 5/7-day schedule. CC-122 will be initiated on Cycle 1 Day 9 and on Day 1 of each cycle thereafter up to a maximum of 24 cycles of CC-122 until PD, unacceptable toxicity or discontinuation for any other reason.

Obinutuzumab will be administered as an IV infusion at a dose of 100 mg on Cycle 1 Day 1 and 900 mg on Cycle 1 Day 2 and 1000 mg on Cycle 1 Days 8 and 15. The dose of obinutuzumab on Days 1 and 2 of Cycle 1 may be adjusted per institutional practice as long as the combined dose equals 1000 mg. Obinutuzumab will be administered at a dose of 1000 mg on Day 1 of Cycles 2 through 6. In the event CC-122 is discontinued prior to obinutuzumab, subjects may continue to receive the protocol-specified total of 6 cycles of obinutuzumab at the discretion of the treating physician. In addition, for subjects that have surpassed the 24 cycles of CC-122, Celgene will continue to provide an additional 3 cycles of CC-122 to allow time for subjects to be switched to commercially available therapies at the discretion of the treating physician.

Please refer to Protocol Section 8 for detailed description of study treatment.

4.3. Stratification and Randomization

This study is an open-label study. Treatment assignment does not require randomization, blinding, or stratification.

4.4. Sample Size Determination

During the Dose Escalation Phase of the study, an intrasubject dose escalation schedule and standard “3 + 3” dose escalation design will be used to identify initial toxicities and safety of single agent CC-122 and to determine the MTD of the combination treatments. The final number of subjects needed in the Dose Escalation Phase depends on number of DLTs observed within each cohort. Non-DLT evaluable subjects withdrawn prior to completion of the DLT evaluation period due to reasons other than DLT will be replaced.

5. GENERAL STATISTICAL CONSIDERATIONS

5.1. Reporting Conventions

General reporting conventions for this study are:

- By default, descriptive statistics in this template include n (the corresponding sample size), Mean, Median, Standard Deviation (StdDev), Minimum (Min), and Maximum (Max). For selected outputs, first quartile (Q1) and third quartile (Q3) will also be displayed. Unless specified in the actual table shells, the mean, median, Q1, Q3 and the upper and lower limits of a two-sided 95% CI should be displayed to one more decimal place than the original data (derived analysis data). Standard deviation and standard error (SE) should be formatted to two decimal places more than the measured value. The minimum and maximum should be displayed to the same number of decimal places as the original data.
- P-values will be presented with 4 decimal places and presented in the format of “0.xxxx” or “<0.0001” or “>0.9999”.
- Summary tables, listings, and any supportive SAS output will include a header of explanatory notes that will indicate the name of the sponsor, protocol number, data cut-off date and the page n of N.
- Summary tables, listings, and any supportive SAS output will include a footer of explanatory notes that will indicate, at a minimum, the following:
- Program source (e.g., SAS program name, including the path, that generates the output).
- Data extraction date (e.g., the database lock date, run date). The purpose of showing the data extraction date is to link the output to a final database, either active or archived, that is write-protected for replication and future reference.
- Output date (appearing on each output page). The output date will indicate the date the output was generated by the analysis program.
- Individual subject listings will display raw data collected in the clinical database and some key derived data used in the analyses.

Other general conventions include:

- The analysis specified by this SAP will include all treatment arms, dose cohorts (different dose levels or regimen), unless otherwise specified. Tables and figures will be summarized by treatment arm, dose cohorts and overall, if applicable.
 - IP, study treatment and study drug are used interchangeably and, if not otherwise specified, are defined as any study-related treatment, including CC-122, ibrutinib, or obinutuzumab.
 - First dose date of IP corresponds to the earliest date any dose (of CC-122, ibrutinib, or obinutuzumab) has been initiated (i.e. a non-zero dose was administered/infused).
 - Last dose date of IP corresponds to the latest date any dose (of CC-122, ibrutinib, or obinutuzumab) has been administered/infused.
- 

Time points beyond Cycle 12 will not be displayed in the by cycle summary due to limited sample size and the allowed flexible frequency of the test/measurement. Data from all time points will be included to evaluate the “most extreme” post-baseline value.

- For subjects in Arm A who have disease progress (PD) and then are treated with Ibrutinib or Obinutuzumab, following conversions will be applied:

- In the database, the cycles after PD/arm switch will be labeled with suffix “-PD” and started from “Cycle 1 Day 1”. For summary and reporting purpose, those visits will be mapped to the cycle numbers based on their original treatment schedule. For example, if a subject switch to Arm B (CC-122 plus Ibrutinib) after Cycle 2, the next visit labeled as “Cycle 1 Day 1 - PD” will be mapped as “Cycle 3 Day 1” and summarized accordingly.
 - Efficacy data collected up to the PD/arm switch, and all safety data collected in the study will be included in the summary under Arm A (and the starting dose level of CC-122 they initially received).
 - For study treatment and exposure summaries, the data collected before the treatment switch will be summarized under “CC-122 xx mg” according to the subject’s initial CC-122 dose, the data collected after the treatment switch will be summarized under “CC-122 + Ibrutinib”, or “CC-122 + Obinutuzumab”, according to which drug the subject received.
 - Subjects who switch the treatment can report AEs which are
 - related to Ibrutinib or Obinutuzumab,
 - leading to discontinuation/reduction/interruption of Ibrutinib or Obinutuzumab.

Those TEAEs will be summarized under Arm A (and starting dose of CC-122 they initially received).

- For subjects in Arm C who are not treated with CC-122:

In the analysis based on Safety population, “Obinutuzumab Only” group will be used to summarize these subjects in Arm C who discontinue treatment/study without treatment of CC-122. In addition, “Arm C Total CC-122” and “Arm C Overall” group will be used to summarize the subtotal results without and with these subjects, respectively. In listings which are related with study drug and safety evaluations, “Arm/CC-122 dose” column will be displayed as “Arm C/0.0 mg” for these subjects.

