11.1. Adverse Events

11.1.1. Summary of Adverse Events

AEs will be analyzed in terms of Treatment-Emergent Adverse Events (TEAEs) which are defined as any AEs that begin or worsen on or after the start of IP through 28 days after the last dose of IP. All AEs will be coded using the MedDRA® dictionary Version 22.0 or higher.

If a subject experiences the same AE more than once with a different toxicity grade, then the event with the highest grade will be tabulated in “by grade” tables. If a subject experiences multiple AEs under the same PT (SOC), then the subject will be counted only once for that PT (SOC). In addition, AEs with a missing intensity will be presented in the summary table as an intensity category of “Missing” and will not be imputed.

The incidence of TEAEs will be summarized by MedDRA SOC and PT. The intensity of AEs will be graded 1 to grade 5 by investigator according to the National Cancer Institute Common Terminology Criteria for Adverse Events (NCI CTCAE) Version 4.03 with the exception of tumor flare (NCI CTCAE version 3.0), tumor lysis [REDACTED] and laboratory abnormalities as recommended by the IWCLL guidelines for the diagnosis and treatment of chronic lymphocytic leukemia [REDACTED] For all other AEs, the intensity will be determined by the investigator as mild (Grade 1), moderate (Grade 2), severe (Grade 3), life-threatening (Grade 4) or death (Grade 5).

Tables summarizing the incidence of TEAEs by dose cohort will be generated for each treatment arm with the following:

- TEAEs;
- TEAEs related to CC-122, other combination drug (ibrutinib or obinutuzumab) and CC-122 and/or other combination drug;
- TEAEs of NCI CTCAE grade 3 or 4 by maximum NCI CTCAE grade;
- TEAEs related to CC-122, other combination drug (ibrutinib or obinutuzumab) and CC-122 and/or other combination drug with NCI CTCAE grade 3 or 4 by maximum NCI CTCAE grade;
- TEAEs with death outcome;

- TEAEs with death outcome related to CC-122, other combination drug (ibrutinib and obinutuzumab) and CC-122 and/or other combination drug;
- Serious TEAEs;
- Serious TEAEs related to CC-122, other combination drug (ibrutinib and obinutuzumab) and CC-122 and/or other combination drug;
- TEAEs leading to discontinuation of CC-122, of other combination drug (ibrutinib and obinutuzumab), of CC-122 or other combination drug, of CC-122 and other combination drug;

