- TEAEs leading to dose reduction of CC-122, of other combination drug (ibrutinib), of CC-122 or other combination drug, of CC-122 and other combination drug;
- TEAEs leading to dose interruption of CC-122, of other combination drug (ibrutinib and obinutuzumab), of CC-122 or other combination drug, of CC-122 and other combination drug.

As well as

- TEAEs by cycle of onset;
- Febrile Neutropenia, TFR, TLS by cycle of onset and overall;
- TEAEs related to CC-122, other combination drug (ibrutinib or obinutuzumab) and CC-122 and/or other combination drug, by cycle of onset;
- TEAE with onset from second to sixth CC-122 cycle leading to dose reduction/discontinuation of CC-122, of other combination drug (ibrutinib and obinutuzumab), of CC-122 or other combination drug, of CC-122 and/or other combination drug;
- TEAE by CC-122 cycle of onset and leading to dose reduction/discontinuation of CC-122, of other combination drug (ibrutinib and obinutuzumab), of CC-122 and/or other combination drug, of CC-122;
- TEAEs by maximum NCI CTCAE grade;
- TEAEs related to CC-122, other combination drug (ibrutinib or obinutuzumab) and CC-122 and/or other combination drug, by maximum NCI CTCAE grade;
- Common ($\geq 10\%$) TEAEs;
- Common ($\geq 20\%$) TEAEs;
- Common ($\geq 10\%$) TEAEs related to CC-122, other combination drug (ibrutinib and obinutuzumab) and CC-122 and/or other combination drug;
- Common ($\geq 20\%$) TEAEs related to CC-122, other combination drug (ibrutinib and obinutuzumab) and CC-122 and/or other combination drug;
- Selected TEAE of interest by aggregated terms;
- TEAEs by PT.

Selected TEAEs/ serious AEs (SAEs) of interest as determined by the mechanism of action, known class effects, or TEAEs observed to date will be summarized by treatment arm and dose cohort, and then grade or cycle of onset. Standardized MedDRA queries (SMQs) will be used in the search strategy for some of the selected AEs of special interest, intending to aid in case identification. The groupings of selected AEs,

described by one phrase or topic term will be determined by clinicians based on SMQ or relevant search terms and provided to statistician, prior to database lock.

The selected TEAEs of interest include:

- Cardiac Failure (SMQ)
- Embolic or Thrombotic Events (SMQ) including ATE (Sub-SMQ), VTE (Sub-SMQ), and Mixed Embolic and Thrombotic Events (Sub-SMQ)
- Hemorrhage (SMQ)
- Interstitial Pneumonitis (SMQ)
- Peripheral Neuropathy (SMQ)
- Tumour lysis (SMQ)

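### Arm A all-causality safety tables after Cycle 1 pool single-agent CC-122 with the period after ibrutinib or obinutuzumab is added, and no such summary is split at the switch

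*SAP*

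**What the plan says.** Protocol 4.1 lets an Arm A subject who progresses on CC-122 add ibrutinib or obinutuzumab while CC-122 continues. The option opens only once the DLT evaluation (Cycle 1 in Arm A) is complete and the combination has been shown safe in this trial.

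SAP 5.1 gives these subjects their own rules:

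- Efficacy is counted only up to the switch.
- Exposure is divided. The earlier part goes under the initial CC-122 dose, and "the data collected after the treatment switch will be summarized under" the combination actually received.
- For safety, "all safety data collected in the study will be included in the summary under Arm A", at the starting CC-122 dose. For events related to the added drug, or leading to action on it, the SAP repeats: "Those TEAEs will be summarized under Arm A (and starting dose of CC-122 they initially received".
- Visits after the switch carry a separate label in the database, but "those visits will be mapped to the cycle numbers based on their original treatment schedule".

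SAP 11.1.1 defines TEAEs as events that "begin or worsen on or after the start of IP through 28 days after the last dose of IP". SAP 5.1 fixes the end of that window: "Last dose date of IP corresponds to the latest date any dose (of CC-122, ibrutinib, or obinutuzumab) has been administered/infused". The planned tables include "TEAEs by cycle of onset" and "TEAEs related to CC-122, other combination drug (ibrutinib or obinutuzumab) and CC-122 and/or other combination drug", together with tables of events leading to reduction, interruption or discontinuation of each drug. SAP 8 adds a by-subject listing of switchers.

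**The concern.** The first primary objective (Protocol 2.1, SAP Table 2) is the safety of CC-122 given alone, measured by the incidence and severity of adverse events. Arm A is the only arm that can answer it. Under the SAP 5.1 rule, an event that first appears on CC-122 plus ibrutinib or obinutuzumab is counted in the same cell as one that appears on CC-122 alone. A reader of the Arm A tables could not tell how much of a later-cycle excess, a worst grade or a CC-122 dose reduction arose on the combination. The Arm A event counts and the single-agent exposure rows would also cover different periods.

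**Working it through.** The plan states no figure for this point, so there is nothing to reproduce. The check has two parts.

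**1. Which Arm A outputs mix the two periods**

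| Output | Content for a switcher | Separated at the switch? |
|---|---|---|
| Efficacy | up to the switch | yes, cut |
| Exposure | before and after, by regimen | yes, split |
| DLT table; Cycle 1 column of by-cycle tables | Cycle 1, before the add-on is allowed | no mixing arises |
| All-causality TEAEs: any, Grade 3/4, serious, fatal | whole study, to 28 days after the last dose of any study drug | no |
| By-cycle TEAEs after Cycle 1 | both periods, cycles renumbered | no |
| TEAEs leading to a CC-122 change, including the table for CC-122 cycles 2 to 6 | both periods | no |
| CC-122-related TEAEs | both periods | no |
| Worst laboratory, vital-sign, ECG and LVEF values | all post-baseline values | no |
| TEAEs related to the partner drug, or leading to its interruption or discontinuation | post-switch only, since no partner drug is given before | yes, in effect |

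SAP 11.1.1 counts a subject once per term, at the highest grade. With a fixed denominator, adding post-switch data can therefore only raise incidence and worst grade or leave them unchanged.

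**2. Size, as an illustration**

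Inputs: N = 20 (Protocol 4.1); infusion reactions in two-thirds of patients at the first obinutuzumab infusion (Protocol 8.2.10.1); with ibrutinib, bleeding of any grade in about half and of Grade 3 or higher in up to 6% (Protocol 8.2.11). The number of switchers k, and which drug they added, are not given. No split by drug is assumed, because Arm A admits subjects with prior BTK-inhibitor therapy.

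- Infusion reactions, (2/3)k/20: for k = 1, 2, 3, 4 this gives 3.3, 6.7, 10.0, 13.3 percentage points. No one is infused before the switch, so each reaction is new to the subject.
- Any-grade bleeding, at most 0.5k/20: 2.5, 5.0, 7.5, 10.0 points. It is a maximum because a subject with an earlier bleed is already counted. Grade 3 or higher: at most 0.06/20 = 0.3 points per switcher.
- Events not isolated by attribution, q(1 − a)/20. Here q is the chance of an event new to the subject after the switch (assumed 0.1 to 0.4) and a is the share attributed to the added drug (assumed 25% to 75%). Low end: 0.1 × 0.25/20 = 0.125 points per switcher. High end: 0.4 × 0.75/20 = 1.5 points.
- Events leading to a CC-122 change, at most q/20: 0.1/20 = 0.5 to 0.4/20 = 2.0 points per switcher. Attribution does not help, because these tables are sorted by action taken. It is an upper bound: not every new event leads to a CC-122 change, and a subject with an earlier change is already counted.

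**Partial dates.** SAP 17.4 cannot be applied unchanged at the switch. When only the day is missing, in a month after the first-dose month, onset is set to the 1st. In a 30-day switch month there are 30 + 29 + … + 1 = 465 pairs of switch day and onset day with onset on or after the switch. Only the 30 pairs with a switch on the 1st stay post-switch, so 435/465 = 94% would move to the single-agent period.

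**The case against.** The rule is openly prespecified and matches the Safety population (SAP 5.2.1), which groups subjects by the arm and CC-122 dose they first received. CC-122 continues after the switch, so pooling captures all toxicity under CC-122. That is a legitimate supportive view, and the pooled tables should stay. But it answers a different question from the single-agent objective. In the same section the SAP already reports by treatment actually received, with an obinutuzumab-only group for Arm C subjects never given CC-122.

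The mitigations are real. Partner-related tables show post-switch events attributed to the added drug. Tables of events leading to partner-drug interruption or discontinuation show others. For Grade 3 or higher thrombocytopenia, for example, Protocol Table 14 begins with holding every study drug, so the event should normally appear there as well. With about 20 subjects, the listings in SAP 8 and 11.1.1 allow onset to be compared with the switch date by hand. What remains is that combination-period events attributed to CC-122 or to neither drug, and the tables of CC-122 changes, have no summary split at the switch. Protocol 8.2.9.1 asks that CC-122 be considered for modification first on a combination, so the latter tables can take in post-switch events whatever their cause.

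It is also true that Arm A sets no MTD or RP2D, that Phase 2 will not proceed, and that no exposure-adjusted event rates are planned, so the mismatch between exposure and event periods enters no calculation. This limits the consequences. It does not supply the missing summary for a primary objective.

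**Conclusion.** The point holds as a gap in the planned summaries and should be fixed. As written, no Arm A all-causality safety table beyond Cycle 1 isolates CC-122 given alone. The reading of the rule is firm; the size is not. It depends on the number of switchers, the drug added and time on the combination, none of which is stated, and with no switchers it is zero. The infusion-reaction and bleeding figures are the best grounded, but they describe events that would largely also appear in the partner-related tables. The figures using q and a rest on assumed ranges.

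Three stronger readings are tempting and not supported:

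- A reader might infer that the DLT results or a dose decision are affected. The add-on opens only after the DLT evaluation, and the NTD and MTD endpoints belong to the combination arms.
- A reader might infer that post-switch events are hidden. The partner-drug tables and the listings show many of them.
- A reader might take 0.5 to 2.0 points per switcher as the expected inflation of CC-122 dose changes. It is a ceiling on an assumed rate.

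**What to change.** In SAP 5.1 and 11.1, before database lock:

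- Keep the pooled Arm A tables. Add single-agent TEAE summaries (any, Grade 3/4, serious, fatal, by cycle, and leading to CC-122 reduction, interruption or discontinuation), cut at the first dose of the added drug, with all Arm A Safety subjects as denominator.
- Show post-switch events under 'CC-122 + Ibrutinib' and 'CC-122 + Obinutuzumab', with switchers as denominator, as exposure already does.
- State that the pre-switch tables address the single-agent objective.
- In the single-agent version, restrict worst laboratory, vital-sign, ECG and LVEF values to those before the switch, with the existing baseline.
- Assign events by onset date. Where a partial onset date or a missing date of worsening leaves the period uncertain, report those events as a separate count and show the single-agent table both with and without them.

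No new data are needed. The work is SAP wording, a period flag built from the first added-drug dose date (visit labels are not enough, because adverse event dates come from log pages) and several extra tables. The SAP should also state the downsides: the post-switch groups will be small, switchers lose the 28-day follow-up tail in the single-agent tables, and toxicity from CC-122 continued after the switch appears only in the post-switch and pooled tables.

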5.2. Analysis Populations

All enrolled subjects will be used to assess subject disposition.

The demographic and baseline characteristics tables will use all populations defined in this section.

Drug exposure and all safety analyses (except for PK) will be based on the Safety population.

All DLTs will be based on the Dose Limiting Toxicity Evaluable population.

Efficacy analyses including Eastern Cooperative Oncology Group (ECOG) performance status (except for PK) will be based on the Safety population. Key Efficacy analyses [summary of ORR, DoR and PFS] will be based on both the Safety population and the Efficacy Evaluable (EE) population.

PK analyses will be based on the PK population.

All listings will use all enrolled subjects.

